4.15 Secondary Endpoints

Secondary endpoints will include the following:

- Adherence to ICS regimen in *Observation* interval (months 4-6)
- Adherence trajectory, as determined by group-based modeling of adherence patterns.
- Change in cACT score from first study visit to the second, third, fourth, and fifth study visits.
- Number of asthma-related emergency room visits, hospitalizations, and oral steroid courses between study conditions.
- Healthcare costs associated with emergency room visits, hospitalizations, and oral steroid courses between study conditions.
- Continued use of sensors in 7-13 month follow-up period (feasibility outcome)

Health system use outcomes will be assessed primarily using CHOP electronic health record data and, secondarily, via caregiver report to account for utilization that may have occurred outside of CHOP. ED visits, hospitalizations, and oral steroids courses will be characterized as asthma-specific using existing, validated asthma registry definitions that include asthma visit diagnoses, medication orders, and asthma pathway order set activation. Costs will be estimated using average insurance payments for asthma ED visits, hospitalizations, and oral steroid courses in addition to the costs of the intervention components (i.e. sensors, incentive value, and research staff support).

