4.17 Sample Size and Power

Our analysis of pilot data demonstrates a 48% difference in ICS adherence when comparing a time interval with financial incentives (the same schema proposed in this study) to a time period without incentives. To ensure a power of 80% at a significance level of 0.05 to detect a more conservative 30% difference in average adherence between arms 1 and 3 in the *Experiment* phase (corresponding to 65% and 35%, respectively), 40 patients are required in each of these two arms. To ensure scientific rigor given the vulnerable nature of the population, we estimate ~20% loss to follow-up. Therefore, we will aim to enroll 50 participants in study arms 1 and 3 and 25 participants in arm 2, or 125 participants total, to achieve sufficient power to detect a difference between arms 1 and 3. The study is not to be powered to detect differences in arms 1 to 2 or 2 to 3 (hence the 2:1:2 randomization schema) or for health outcomes or cost offset; rather, it is intended to obtain preliminary estimates of marginal effects of the intervention components and effect sizes on utilization outcomes by comparing arm 1 to 2 and 2 to 3 to power a future multicenter study. Baseline data reveals that ~50% of children with at least 2 prior hospitalizations have a repeat ED visit or inpatient stay 6 months after the 2nd hospital discharge.

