4.18 Additional analyses

Hypothesis 1.2 Longer time intervals to next asthma-related ED or inpatient visit, and reduced healthcare use and costs, will be observed in Arm 1 compared to Arms 2 and 3 (and in Arm 2 compared to Arm 3).

Time to next asthma-related ED or inpatient visit from enrollment will be first modeled using the Kaplan-Meier plots. Study arms will be compared using log-rank tests and unadjusted Cox proportion hazards models. Adjusted hazard models will include the additional covariates described above and the Anderson-Gill method will be used to account for recurrent events. Total medical costs will be estimated for the 12 months following study enrollment, accounting for each asthma-related ED visit and hospitalization, as well as the expenses incurred with study participant incentives, sensors, and use of the WTH automated platform. We predict that intervention will reduce medical costs, thereby contributing to a *cost offset*. We will estimate potential savings in medical costs by calculating the difference in average total medical costs minus study-related expenses between study arms.

Aim 2. Assess proposed mechanisms by which intervention strategy influenced adherence trajectory.

Aim overview: The broad goal of this aim is to assess which participant and study characteristics are associated with different longitudinal adherence trajectories.

Characteristics to be examined include baseline factors (demographic, clinical, and prior health utilization factors), intervention strategy (study arm), and potentially modifiable behavioral characteristics. Of specific interest is how intervention strategy in the Experiment phase (study arm) influences child asthma self-efficacy, shared medication responsibility, and medication habit over time and how these characteristics vary with longitudinal ICS adherence trajectories. [Figure 4]

Hypothesis 2: Increases in (1) participant self-efficacy, (2) shared medication responsibility, and (3) habit score will partially mediate the relationship between study arm and sustained adherence trajectory.

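### The total medical costs and cost offset in 4.18 omit the controller inhaler that the intervention aims to make children use more, and the 4.18 cost list conflicts with 4.15

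*Combined protocol and SAP*

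**What the plan says.** Section 4.15 (Secondary Endpoints) defines the cost endpoint as the cost of three kinds of event: "Costs will be estimated using average insurance payments for asthma ED visits, hospitalizations, and oral steroid courses". To these it adds what the intervention itself costs, namely the sensors, the value of the incentives and the support given by research staff.

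Section 4.18 (Additional analyses, Hypothesis 1.2) sets the horizon: "Total medical costs will be estimated for the 12 months following study enrollment". It then lists the contents: "accounting for each asthma-related ED visit and hospitalization, as well as the expenses incurred with study participant incentives, sensors, and use of the WTH" (the last item is the Way to Health platform). It states the expected direction, "We predict that intervention will reduce medical costs", and gives the estimator: "We will estimate potential savings in medical costs by calculating the difference in average total medical costs minus study-related expenses between study arms".

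Section 4.17 plans for mean adherence of 65% in Arm 1 and 35% in Arm 3 during the Experiment phase. It also says that the study is not powered for cost offset.

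**The concern.** Section 4.18 presents its sum as a total and draws an offset from it. The sum leaves out the ICS or ICS/LABA inhaler. Raising use of that inhaler is the trial's primary aim, so this is a medical cost that should differ by arm if the intervention works. Acute care, which the plan expects to fall, is counted. A reader of the result would take the offset as net of all asthma-related medical cost, and it would not be.

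The two sections also disagree about what is counted. Two analysts, one working from 4.15 and the other from 4.18, would report different cost differences from the same data.

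**Working it through.** **The two lists side by side**

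| Item | 4.15 | 4.18 |
|---|---|---|
| Asthma ED visits, hospitalizations | yes | yes |
| Oral steroid courses | yes | not listed |
| Incentives, sensors | yes | yes |
| Research staff support | yes | not listed |
| Way to Health platform | not named | yes |
| Controller inhaler | not listed | not listed |
| Rescue inhaler | not listed | not listed |
| Outpatient visits without oral steroids | not listed | not listed |

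**Source of the adherence difference.** The plan states no cost figure to reproduce. The 65% and 35% come from the sample size in 4.17, which does reproduce with the unpooled two-proportion formula (two-sided 0.05, 80% power): [0.65 × 0.35 + 0.35 × 0.65] × (1.960 + 0.842)² / 0.30² = 0.455 × 7.85 / 0.09 = 39.7, so 40 per arm. With 20% loss, 40 / 0.80 = 50.

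**Extra controller use, Arm 1 minus Arm 3.** The 2 and 4 daily puffs are the regimens that 3.1.3 uses to set the incentive. The Experiment phase is taken as 90 days.
- 4 puffs a day: 0.30 × 90 × 4 = 108 puffs per child.
- 2 puffs a day: 0.30 × 90 × 2 = 54 puffs per child.
- Ratio of use: 0.65 / 0.35 = 1.86.

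**Cost of that use.** The documents give no inhaler size or price. Assumed: 120 puffs per inhaler and a payment of $50 to $300. Then 54 / 120 = 0.45 and 108 / 120 = 0.90 inhaler. A payer's cost rises only by the share of the extra use that becomes extra dispensing, so that share is varied too.

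| Share dispensed | Lowest (0.45 × $50) | Highest (0.90 × $300) |
|---|---|---|
| 100% | $22.50 | $270 |
| 50% | $11.25 | $135 |
| 0% | $0 | $0 |

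These figures cover months 1–3 only. A difference that persisted into the Observation phase would add to them.

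**Comparison with an item that is counted.** The Arm 1 incentive is at most 3 × $30 = $90 per child, and 0.65 × $90 = $58.50 at the planned adherence. With full dispensing, the omitted cost passes $58.50 once an inhaler costs more than $58.50 / 0.90 = $65 (4 puffs a day) or $58.50 / 0.45 = $130 (2 puffs a day).

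**What could cancel it.** Suppose a rescue inhaler costs $25 to $50 (assumed). At 4 puffs a day with full dispensing, Arm 1 would have to use between 0.90 × $50 / $50 = 0.9 and 0.90 × $300 / $25 = 10.8 fewer rescue inhalers per child than Arm 3 to offset the omitted controller cost.

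**The case against.** A reader might infer that the offset is plainly biased in favour of Arm 1, by an amount proportional to the adherence gain. The documents do not support that, for two reasons.

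- **Other items are missing too.** Rescue inhalers and outpatient visits without oral steroids are in neither list, and 4.18 also leaves out oral steroid courses. Better control should lower all of these, so omitting them works against Arm 1.
- **Payment follows dispensing.** The inhaler is already prescribed (3.4.1), and all arms have a medication refill check at Visits 2 and 3 (4.5, 4.6). Dispensing may differ between arms by less than use does, possibly not at all.

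Two further inferences also fail. The 4.15 endpoint is openly labelled as the cost of ED visits, hospitalizations and oral steroid courses, so leaving out controller cost does not bias it as defined. And 4.17 ties the future multicenter study to component effects and utilization effect sizes, not to the cost offset.

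Materiality is also open. The documents give no payment for an ED visit or admission, so it cannot be shown that the omission would change the sign of the offset.

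All of this stands, and it limits the claim. It does not remove the two textual facts: 4.18 calls an incomplete sum a total, and its list differs from that in 4.15.

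**Conclusion.** The concern holds for 4.18 in a limited form. The sum is not total medical cost, and the offset drawn from it is likely overstated for Arm 1 to the extent that extra controller use becomes extra dispensing. The net direction is likely but not proven.

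The omitted controller cost is $0 to about $270 per child over the Experiment phase. That range rests on the planned 30-point difference, 2 to 4 puffs a day, and the assumed inhaler size, price and dispensing share. The conflict between the two lists needs no assumption. This affects a secondary, unpowered result only; the primary adherence comparison is untouched.

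**What to change.** 1. Use one cost list in 4.15 and 4.18: asthma ED visits, hospitalizations, oral steroid courses, and all intervention components, including the platform and staff support.
2. Report the offset with and without asthma drug cost, covering both controller and rescue inhalers so that the addition is not selective. Value drug use as recorded actuations times an average payment per actuation of the product, for months 1–6.
3. Show controller cost with both capped and uncapped actuations. Puffs above the prescribed dose still consume drug. But only Arm 1 is paid per actuation, and 4.14 anticipates gaming, so uncapped counts could charge non-therapeutic puffs to that arm.
4. Show a range for the share of use that becomes dispensing.
5. If drug cost is not added, rename the 4.18 sum as acute-care plus intervention cost, and do not present the difference as a total cost offset.

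**Cost.** A price table and revised wording; both inhalers are already monitored electronically. The stated offset may look less favourable. Drug cost would cover months 1–6 of a 12-month horizon, because later sensor data are kept only where available (3.1.4). Covering the full horizon from refills needs a new chart item, since 4.11.1 abstracts refills for the prior year only.

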4.16 Statistical Methods

4.16.1 Baseline Data

Baseline and demographic characteristics will be summarized by standard descriptive summaries (e.g. means and standard deviations for continuous variables such as age and percentages for categorical variables such as gender).

4.16.2 Efficacy Analysis

We will assess the effectiveness of randomization by comparing the study arm balance on key demographic, clinical, and past health care utilization variables using analysis of variance (ANOVA) and t-tests or the nonparametric equivalent for continuous variables and chi-square tests or Fisher exact tests for categorical variables.

Primary analysis: Our primary outcome will be monthly ICS adherence in months 0-3 (Experiment Phase). Secondary outcomes will include monthly ICS adherence in months 4-6 (Observation Phase), asthma control at the end of the Experiment and Observation period. Secondary outcomes will also include monthly ICS adherence in months 7-13 (follow up period) to assess feasibility and acceptability of longer durations of electronic monitoring. We will consider arcsine transformation on the ICS adherence outcomes as necessary. This technique is commonly used for proportion data. We will use generalized estimating equations (GEE) to adjust for within-subject correlations due to repeated measures for the study's primary and secondary monthly adherence outcomes. Models will include main effects for arm and time (month) and arm-by-month interaction terms to allow for differing ICS adherence over time between arms. The dependent variable of monthly ICS adherence will be defined as mean daily observed-to-prescribed ICS actuation proportion for each study month. Mean daily adherence proportion will be capped at 1, such that participants taking more than their prescribed daily dose cannot receive "extra credit" for doses taken on those days. All statistical tests will be 2-sided. A P-value <0.05 will be considered statistically significant.

Secondary analysis: We will construct adherence trajectories for the combined *Experiment + Observation* interval for each study participant using group based trajectory modeling (GBTM). This modeling approach accounts for changing behavior over time and allows for identification of several distinctive developmental progressions without imposing the requirement that they vary normally about the population mean.^{21,22} Thus, participants with similar daily adherence trajectories are grouped about similar longitudinal trends and the model output is probabilistic assignment of each individual to one of several (up to six) adherence groups. Based on group-based modeling research on medication adherence from other conditions, anticipated ICS trajectory groupings will likely include: (1) severe early non-adherence, (2) severe delayed non-adherence, (3) moderate or episodic non-adherence, and (4) sustained adherence.^{23,24} (See Figure 3 for a preliminary 3-group ICS adherence trajectory model from our prior work.) Adherence group/category will then become the dependent variable for subsequent analysis in which a multinomial or ordered logistic regression will be applied with treatment arm as the exposure, adjusting for the covariates

[figure not shown]

Figure 3: 30-day post-discharge ICS adherence trajectories. (From Kenyon, et al. *J Asthma*. 2018.)

described above. For each adherence trajectory group, relative risk ratios for arms 1 and 2 compared to arm 3 will be calculated. We will test for overall effect of treatment arm on adherence trajectory in addition to important permutations (i.e. Arm 1 compared to Arm 3 within sustained adherence trajectory) using chi-square tests and generate marginal estimates of the probability of trajectory group membership, given treatment arm assignment (e.g. the probability of being in the sustained trajectory group if randomized to Arm 1 vs Arm 2 vs Arm 3). Findings presented alongside the primary analysis of observed-to-prescribed interval adherence percentage.

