3.1.2 Run-in Phase (Month 0)

The study will be broken down into three discrete phases: (1) *Run-in* (2) *Experiment*, and (3) *Observation* (Figure 2). During the *Run-in* phase, every caregiver-child dyad will have access to the inhaler sensor app and will receive electronic ICS use monitoring. ICS use will be monitored using an electronic sensor that affixes to their ICS inhaler and will remain through the study *Observation* phase. Participants will be sent 4 text messages, each designed to elicit a response from the caregiver about the study technology or the study itself. (See Appendix 1 for content of the Run-in text messages) Participants for whom any inhaler use data is transmitted to the study platform within the first 2 weeks of the Run-in Phase AND reply to one or more of the 4 text messages sent from the study platform (“Responders”) will be randomized into one of three arms at the end of the Run-in phase. (see section 4.10 for details on procedures for “Non-responders”) The second two weeks of the Run-in Phase is designed to provide baseline adherence data.

[figure not shown]

Figure 2: Study schema for proposed RCT

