3.1.3 Experiment Phase (Months 1-3) and Observation Phase (Months 4-6)

The three experimental conditions will be: financial incentives, adherence reminders, and feedback (Arm 1); adherence reminders and feedback without incentives (Arm 2); or electronic monitoring alone (Arm 3). The financial incentives in Arm 1 will consist of 3 months of fixed-ratio incentives for each ICS actuation (i.e. 25 cents per puff for children on 4 daily ICS doses and 50 cents per puff for children on 2 daily doses), with a maximum of \$1 per day. With regard to the reminders and feedback in Arms 1 and 2, study participants will receive automated daily text message or push notification reminders and automated weekly feedback summarizing their adherence performance through Way to Health, a mobile health, electronic monitoring platform (described below in section 4.1). At the end of the first month of the experiment phase, families will be contacted by study staff to complete a follow-up survey that will reassess disease control, medication supply, and intentions and behaviors with

regard to ICS use (study visit 2). After the experiment interval, families will be contacted again by study staff to complete a follow-up survey and a semi-structured interview (study visit 3). At this point, all reminders, feedback, and incentives will cease, but daily ICS use monitoring will continue with the electronic sensors for all study arms (*Observation* phase) to assess for enduring effects. There will be a fourth study visit in the 7th study month, when study surveys will be completed, and a fifth and final study visit at one year assessing asthma control and health care utilization outside of the CHOP system.

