4.4 Study Experiment Phase (Phase 2)

The child-caregiver dyads will be randomized into one of three arms for months 1-3: (1) receiving daily reminders, weekly feedback, and incentives, (2) receiving reminders and weekly feedback without incentives, or (3) receiving no reminders, feedback, or incentives. Participants will not know which group they are randomized to until they begin this phase of the study. Study participants will be contacted by telephone call or text message to inform them to which study arm they were randomized. At this time, study staff will help participants randomized to Arm 1 select an adherence reward goal of \$30 value.

4.5 Visit 2 (clinic or home preferred, telephone if not possible) – month 2

- Study visit 2 survey question blocks (see section 4.11.2)
- Equipment and medication refill check

4.6 Visit 3 (clinic or home preferred, telephone if not possible) – month 4

- Study visit 3 survey question blocks (see section 4.11.2)
- Semi-structured interview on intervention experiences and preferences
- Equipment and medication refill check

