4.14 Primary Endpoint

The primary outcome will be adherence to ICS regimen both during the *Experiment* interval (months 1-3). Adherence over these study intervals will be characterized as a daily observed-to-prescribed ICS adherence proportion averaged by study month. To operationalize this, a daily medication use log composed of 180 sequential ICS use observations will be generated, representing the count of ICS doses taken each day of study enrollment. These daily counts will be converted into proportions by dividing by the daily prescribed dose and imposing an upper limit of 1 in order to prevent doses taken above the prescribed limit – either during the use of flare plans or attempted “gaming” of the incentives by the participants – from influencing interval adherence estimates. Observed actuations will be quantified using electronic sensors.

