7 STUDY ADMINISTRATION

7.1 Treatment Assignment Methods

7.1.1 Randomization

At the time of enrollment, patients will be assigned to one of three arms using a 2:1:2 block randomization scheme with a block size of 50. Randomization will be accomplished automatically by the Way to Health web-based platform. During the Run-in interval of the study, every caregiver-child dyad will receive electronic ICS use monitoring. Participants for whom we received any adherence monitoring data and at least one text message reply by the end of week 2 will be randomized into one of three experimental conditions at the end of the Run-in period.

Participants will be randomized using block randomization, so arms 1 and 3 will have approximately equal sample sizes and arm 2 will have approximately half the number of

participants(as the study is powered to detect a difference between arms 1 and 3). A total n of 125 will be randomized, with a recruitment goal of about 50 in arms 1 and 3 and 25 in arm 2.

[figure not shown]

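### Section 4.16.2 gives the primary outcome window as months 0-3, but month 0 is the pre-randomization Run-in; the window should read months 1-3 and the Arm 1 versus Arm 3 contrast of 4.17 should be carried into the model section

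*Combined protocol and SAP*

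**What the plan says.** The primary analysis paragraph of 4.16.2 states: "Our primary outcome will be monthly ICS adherence in months 0-3 (Experiment Phase". The rest of the plan numbers the phases differently:

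- 3.1.2 heads the Run-in as month 0. All dyads are monitored, and randomization comes at its end. On the use of these data it says: "The second two weeks of the Run-in Phase is designed to provide baseline adherence data". Section 3.2 describes the same two weeks as baseline collection.
- 3.1.3 is headed "Experiment Phase (Months 1-3) and Observation Phase (Months 4-6", and Table 1 shows the same months.
- 4.4 says: "The child-caregiver dyads will be randomized into one of three arms for months 1-3".
- 4.14, the primary endpoint section, places the outcome in the Experiment "interval (months 1-3). Adherence over these study intervals will be characterized" as a daily proportion averaged by study month.

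On the model, 4.16.2 specifies GEE and says: "Models will include main effects for arm and time (month) and arm-by-month interaction terms". It sets a two-sided 0.05 level but does not say which term or contrast is the primary test, or what part month 0 plays.

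The comparison of interest appears elsewhere. Section 4.17 sizes the trial for a "more conservative 30% difference in average adherence between arms 1 and 3" in the Experiment phase (65% against 35%), and 7.1.1 explains the allocation ratio "as the study is powered to detect a difference between arms 1 and 3".

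**The concern.** The endpoint section and the analysis section give different windows for the primary outcome. The extra month in 4.16.2 is a real study month with sensor data, so an analyst could follow that sentence literally.

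The window also decides what the listed model terms mean. With month 0 in the model as reference level, the arm coefficient is a difference that precedes the intervention, and the treatment effect sits in the interaction. With months 1-3 only, the arm coefficient is the month 1 effect, and the interaction tests only whether the effect changes over time. Because 4.16.2 does not name the contrast, someone working from that section alone could not tell which result answers the primary question.

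**Working it through.** **1. Which window is meant.** Table 1, 3.1.3, 4.4 and 4.14 give months 1-3. Section 4.16.2 itself labels its window as the Experiment phase and goes on to months 4-6 and 7-13, which is the same study-month numbering. The 180-day log in 4.14 equals 6 x 30 days and fits months 1-6; months 0-6 would need 7 x 30 = 210. The opening of 7.1.1 speaks of assignment at enrollment, but the same paragraph, 3.1.2 and 3.2 put it after the Run-in, and 4.4 says families do not learn their arm until the Experiment phase starts. The expected arm difference in month 0 is therefore zero.

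**2. What the listed terms estimate.** Take a constant 30-point Arm 1 minus Arm 3 effect in months 1-3 and zero in month 0, with the first month in the model as reference level. Write b for the arm coefficient and g(m) for the arm-by-month coefficient at month m.

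| Months in model | b | each g(m) | Months 1-3 average difference |
|---|---|---|---|
| 0-3 | 0 | 30 | b + [g(1)+g(2)+g(3)]/3 = 30 |
| 1-3 | 30 | 0 | b + [g(2)+g(3)]/3 = 30 |

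The single coefficients trade places. The average over months 1-3 is 30 points either way.

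**3. The plan's own sample size.** Inputs from 4.17 and 4.16.2: 65% and 35%, 80% power, two-sided 0.05. Unpooled two-proportion formula: n = (1.960 + 0.842)² x (0.65 x 0.35 + 0.35 x 0.65) / 0.30² = 7.849 x 0.455 / 0.09 = 39.68, so 40 per arm. With 20% loss, 40/0.8 = 50, and 50 + 25 + 50 = 125. The stated figures are reproduced.

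**4. Size if month 0 were averaged in with equal weight.** (0 + 30 + 30 + 30)/4 = 22.5 points.

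The documents give no SD, so I assumed SDs for the months 1-3 mean and used a two-sided t-test (noncentral t) at 40 per arm. With equal monthly variances and between-month correlation r:

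- SD of the four-month mean = SD x sqrt{[(1+3r)/4] / [(1+2r)/3]}.
- Monthly SD = SD / sqrt[(1+2r)/3]. For a 0-1 variable with mean 0.65 or 0.35 this cannot exceed sqrt(0.65 x 0.35) = 0.477, which sets a lowest possible r for each SD.
- The SD implied by 40 per arm: 80% power needs a standardized difference of 0.634, and 0.30/0.634 = 0.473.

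| SD (assumed) | r considered | Power, 30 points | Power, 22.5 points |
|---|---|---|---|
| 0.30 | 0.3 to 1.0 | 99% | 94% to 91% |
| 0.35 | 0.31 to 1.0 | 97% | 85% to 81% |
| 0.40 | 0.56 to 1.0 | 91% | 72% to 70% |
| 0.473 | 0.975 to 1.0 | 80% | about 56% |

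For the last three rows the lower end of r is the feasibility limit. The last row requires nearly all-or-none adherence that hardly varies between months.

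**5. Run-in adherence as a covariate.** The outcome variance remaining is 1 - c², where c is its correlation with the months 1-3 mean. The documents do not give c. At assumed values of 0.5 and 0.7, 0.75 and 0.51 of the variance remain.

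**The case against.** The best defence is that this is a wrong digit that the document itself corrects. The sentence carries the Experiment phase label, and that phase is months 1-3 everywhere else. I accept this as the likely intent. It still leaves the primary outcome stated two ways, and the section an analyst would program from is the one in error.

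A reader might infer that the plan has no primary contrast. The documents do not support that. Section 4.17 names Arm 1 versus Arm 3 in average Experiment-phase adherence and says the other pairs are not powered. Section 4.16.2, in its secondary analysis text, describes the primary analysis as one of interval adherence. The gap is only that the primary analysis paragraph does not repeat the contrast. Nothing says that the arm coefficient at a reference month would be the test.

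A reader might also infer that the trial will lose power. That requires equal-weight averaging over months 0-3, which no section prescribes. The month-specific terms keep month 0 separable, and any contrast confined to months 1-3 is undiluted.

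Finally, keeping month 0 in the model as a baseline reference level is a legitimate alternative to a covariate, provided the contrast is stated.

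**Conclusion.** The point stands as an inconsistency in the definition of the primary outcome, with a clear likely answer: months 1-3. It should be fixed, because the analysis section neither matches 4.14 nor carries over the contrast of 4.17, and its listed terms depend on the window.

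The size is conditional. Under equal-weight averaging, which I do not take to be intended, the effect falls by a quarter, to 22.5 points. The power loss runs from a few points (SD 0.30) to about 24 points (80% to 56%, SD 0.473). These figures rest on assumed SDs, equal monthly variances, a constant effect over months 1-3 and no difference in month 0.

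The error would bias toward no effect. A reader might infer a risk of a false positive, but a month with zero expected difference does not create one. Nor is the sample size wrong: 40 per arm and 125 in total follow from the stated inputs. Leaving out the baseline covariate costs precision and causes no bias.

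**What to change.** In 4.16.2:

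1. Change months 0-3 to months 1-3.
2. State the primary test as the Arm 1 minus Arm 3 difference in adherence averaged over months 1-3, estimated from the GEE, consistent with 4.17.
3. State that month 0 is not an outcome month, and enter adherence in the last two Run-in weeks as a baseline covariate.

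The cost is wording in one section and one added model parameter. The Run-in data are already collected for this purpose, and enrollment, visits and sample size are unaffected.

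### The GEE plan names no small-sample method for about 40/20/40 children: Arm 1 vs 3 is little affected, but a joint arm-by-month test could run well above 0.05

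*Combined protocol and SAP*

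**What the plan says.** Section 4.16.2 (Efficacy Analysis) applies one method to all primary and secondary monthly adherence outcomes: "We will use generalized estimating equations (GEE) to adjust for within-subject correlations due to repeated measures". On the mean model it says "Models will include main effects for arm and time (month) and arm-by-month interaction terms". On testing it says "All statistical tests will be 2-sided" and "A P-value <0.05 will be considered statistically significant".

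It does not state the working correlation, whether standard errors are robust or model-based, whether tests are Wald or score, the reference distribution, whether month is categorical or linear, or which contrast is the primary test.

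Section 4.17 (Sample Size and Power) gives the numbers: "40 patients are required in each of these two arms" (Arms 1 and 3), then about 20% loss, so "we will aim to enroll 50 participants in study arms 1 and 3 and 25 participants in arm 2". It powers only Arm 1 against Arm 3. Comparisons with Arm 2 are to give preliminary estimates for a later multicenter trial.

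The primary window is months 1-3 in section 4.14 and months 0-3 in section 4.16.2. Months 7-13 are a secondary outcome in 4.16.2, included to judge the feasibility and acceptability of longer monitoring.

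**The concern.** The usual GEE standard error is the robust (sandwich) one, read against a normal or chi-square distribution. It is justified when the number of independent units, here children, is large. With few children the residuals are too small because each arm's own mean has been fitted, and the chi-square reference ignores the uncertainty in the estimated variance. Both errors make p-values too small and intervals too narrow.

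The problem is mild for one contrast between two arms of 40. It grows when an arm has only 20 children, and grows further when many contrasts are tested jointly, because a whole covariance matrix is then estimated from those 20.

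At stake are the Arm 2 comparisons meant to inform a later trial, and any statement that the arms follow different courses over time.

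**Working it through.** **Inputs from the documents.** Two-sided 0.05 (4.16.2); 80% power, 65% against 35%, 40 evaluable in each of Arms 1 and 3, about 20% loss, 50/25/50 enrolled (4.17); GEE with arm, month and arm-by-month terms (4.16.2).

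**The plan's own figure.** Two proportions, unpooled variance:

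n = (1.960 + 0.842)² × (0.65×0.35 + 0.35×0.65) / 0.30² = 7.849 × 0.455 / 0.09 = 39.7, so 40 per arm. Then 40/0.80 = 50. The stated sample size reproduces. The same loss in Arm 2 gives 25 × 0.80 = 20, a number the plan does not state.

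**Assumptions, because the documents give no SD or correlation.** Complete data; no true arm difference; normal or U-shaped outcomes; within-child correlation exchangeable at 0.6 or first-order autoregressive at 0.7. Results barely moved across these.

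**Degrees of freedom with categorical month.** (3 arms − 1) × (months − 1): 2×2 = 4 for months 1-3, 2×3 = 6 for months 0-3, 2×6 = 12 for months 7-13.

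**Test examined.** With every arm-month mean free and complete data, the GEE estimates b are the arm-month means. The uncorrected sandwich for an arm of n children is V = Σrr′/n², where r is a child's residual vector. For contrasts C, W = (Cb)′(CVC′)⁻¹(Cb) is compared with chi-square. On average V is too small by 1/n: 2.5% for 40 children and 5% for 20.

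**Analytic anchor for Arm 1 vs 3.** With normal data and equal arms of 40, rejecting when W > 1.960² is the same as rejecting when |t| on 78 df exceeds 1.960 × √(39/40) = 1.935. That probability is 5.7%.

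**Simulated false-positive rates, uncorrected sandwich, Wald chi-square, 40/20/40:**

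| Test | Rate |
|---|---|
| Arm 1 vs 3, average adherence (1 df) | about 5.5-6% |
| Contrasts with Arm 2 (1 df) | about 6-7% |
| Three-arm main effect (2 df) | 6.4-7.4% |
| Arm-by-month, months 1-3 (4 df) | 7.9-8.5% |
| Arm-by-month, months 0-3 (6 df) | 9.5-10.0% |
| Arm-by-month, months 7-13 (12 df) | 17.3-18.3% |

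Full GEE fits in standard software (exchangeable working correlation; 1,500 and 1,000 runs) gave 8.4% for months 1-3 and 16.2% for months 7-13. With no loss (50/25/50) the arm-by-month rates are 7.3-7.4% and 14.1-14.9%.

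**Other readings the plan leaves open, 40/20/40:**

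- Linear month, same uncorrected Wald test (2 df): 6.9% for months 1-3, 6.6% for months 7-13.
- Generalized score test, categorical month: 4.7% and 3.4%.
- Model-based variance with the correct working correlation: 5.6% and 3.3%.

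**After correction, 40/20/40.** A Mancl-DeRouen variance with a t reference puts single contrasts at 4.4-5.3%. Small-sample scaling with an F reference brings the joint test to about 5.5-6.5% in the primary period. Over months 7-13 it stays at about 7-11%, depending on the form of scaling and F reference. A pooled unstructured-covariance F test gives 5.0% there.

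**Cost in interval width** (Mancl-DeRouen, equal SDs, two-arm df). Arm 1 vs 3: (40/39) × (1.991/1.960) = 1.042. Arm 1 vs 2: √{[(1/40)(40/39)² + (1/20)(20/19)²] / (1/40 + 1/20)} × (2.002/1.960) = 1.044 × 1.021 = 1.066. These are about 4% and 7%.

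**The case against.** The strongest reply is that the criticised method is not written in the plan. Section 4.16.2 says GEE and stops. A score test, or a model-based variance with the right working correlation, fits that wording and shows no marked inflation. The interaction terms are introduced to let the arms differ over time, which describes the mean model; no joint interaction test is promised. The 4-, 6- and 12-df tests exist only if month is categorical. The powered comparison is average adherence in Arm 1 against Arm 3, where the excess is under one to about one percentage point. Arm 2 contrasts are declared unpowered and preliminary. Months 7-13 serve feasibility, and section 3.1.4 makes that monitoring conditional on data being available.

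Most of this stands. A reader might infer that the trial's 0.05 level fails in general, or that 17% is the error rate of a planned test. The documents support neither: they do not specify the test that produces those rates, and the comparison the trial is built on is nearly unaffected.

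The gap itself remains. The robust variance with a Wald test is the usual way to run GEE, and an analyst would not ordinarily correct it unless told to. The plan leaves open choices whose rejection rates on the same 12-df question run from about 3% to 18%, which is a reason to fix the choice beforehand.

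**Conclusion.** The concern holds in a limited form and is a cheap improvement, not a flaw in the primary comparison. Under an uncorrected sandwich, Wald chi-square and 40/20/40 complete data, the false-positive rate is about 5.5-6% for Arm 1 vs 3 and 6-7% for Arm 2 contrasts. If month is also categorical, a joint arm-by-month test runs at about 8% (months 1-3) to 10% (months 0-3), and about 17% in months 7-13. With linear month the joint test falls to about 7%.

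The points that matter are the Arm 2 contrasts and any joint claim that arms differ over time. The figures rest on an assumed spread and correlation, to which they are insensitive, and on a derived 20 children in Arm 2. Fewer children or incomplete months were not part of these figures.

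**What to change.** In section 4.16.2, keep GEE and add:

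1. The primary contrast, the coding of month and the working correlation.
2. Standard errors from a small-sample corrected sandwich variance (for example Mancl-DeRouen or Kauermann-Carroll), with a t or F reference on between-child degrees of freedom. State how the F denominator is set for joint tests.
3. If a joint arm-by-month test over months 7-13 is reported, a generalized score test, a permutation test of arm labels, or an F test from a repeated-measures model with pooled unstructured covariance. The corrected sandwich alone does not bring that test to 5%.

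The primary window should also be made the same in sections 4.14 and 4.16.2, since it sets the degrees of freedom of any joint test.

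The cost is a few sentences and a software option. Intervals become about 4% wider for Arm 1 vs 3 and about 7% wider for Arm 2 contrasts. The score test is somewhat conservative over seven months (3.4%). No further children or data are needed.
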